1.0 Objectives / Specific Aims

Aim 1: Modify Alcohol and Sexual Assault Prevention (ASAP) content to an eHealth format to include personalized content for each risk group (1. cisgender heterosexual men; 2. cisgender heterosexual women; and 3. sexual and gender minorities).

Aim 1a: Assess normative behaviors ($n = 750$) regarding alcohol use and SA for feedback from Arizona State University (already completed and de-identified data being analyzed) and Georgia State University.

Aim 1b: Adapt and assess initial acceptability of a workbook version of the intervention content among key stakeholders (college administrators and students from each risk group [$n=5$ from each group]) from Arizona State University (already completed and de-identified data being analyzed) and Georgia State University.

Aim 2: Open Pilot Trial. Obtain usability of ASAP among 30 students who engage in HED (10 from each risk group) in an open pilot trial at Arizona State University (already completed and de-identified data being analyzed) and Georgia State University.

Aim 3: A pilot to assess effect size and variability for planning a randomized trial in the future. This Aim will only be conducted at Arizona State University. Randomize students who engage in HED to ASAP or control condition to observe preliminary effect sizes and estimate the variability using a 3-month follow-up. Sample size was determined to estimate the variability within a reasonable margin of error. This calculation also accounted the low base rates of SA and 20% attrition. This led to a sample size of 162 students ($n=54$ from each risk group).

By accomplishing these aims, we will have established the research team, programming, feasibility and preliminary efficacy of the research protocol. If promising, this study will lay the groundwork for an R01 application to test the efficacy of ASAP.

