Aim 3: Upon agreeing to participate in the study, participants will be automatically re-directed to complete a 30-minute online survey regarding their demographics, alcohol use, sexual assault experiences, and bystander experiences and attitudes (Aim 3 Baseline Survey). Upon completing the survey, they will be randomly assigned to either receive the personalized feedback intervention (described above) or to an assessment only control condition. If they were assigned to receive the personalized feedback intervention, they will be automatically directed to receive the personalized feedback intervention (described above). This intervention will take approximately 15 minutes to complete. Immediately following the intervention, they will complete a 15-minute post-intervention survey regarding their feedback and immediate potential outcomes (post-intervention survey). A total of 162 eligible participants will be paid \$25 for completing the baseline portion of the study. Upon completing the post-intervention survey, they will be given local resources regarding alcohol use, sexual assault, and mental health resources (see Resources). All participants will be given this information, regardless of their risk. Participants will be given the option of contacting the study staff if they are distressed by the study procedures. Members of the research team are licensed clinical psychologists and are well-equipped to follow-up with individuals in need. As been the case with our previous studies, we will establish a schedule in which members of the research team will be on call 24 hours a day, seven days a week to address urgent matters. If a participant is distressed and wishes to talk with a member of the research team, the clinical psychologist team member will be available at all times during the study period. The procedure will be the same for Arizona State University student and administrator participants except student participants will be compensated for their time and administrators will be volunteering their time.

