Participants will be contacted 3 months after completing the initial survey in an email (Aim 3 Follow-Up Email) with their PIN. The follow-up survey will be exactly the same as the baseline survey, except time periods will include the “past 3 months” for questions. Participants will have one month to complete the survey and will be sent reminder emails if they have not completed the survey. Upon completing the survey, they will be emailed an e-gift card for \$35 for completing the survey. Upon completing the survey, they will be given local resources regarding alcohol use, sexual assault, and mental health resources (see Resources). All participants will be given this information, regardless of their risk. Participants will be given the option of contacting the study staff if they are distressed by the study procedures. Members of the research team are licensed clinical psychologists and are well-equipped to follow-up with individuals in need. As been the case with our previous studies, we will establish a schedule in which members of the research team will be on call 24 hours a day, seven days a week to address urgent matters. If a participant is distressed and wishes to talk with a member of the research team, the clinical psychologist team member will be available at all times during the study period. The procedure will be the same for Arizona State University student and administrator participants except student participants will be compensated for their time and administrators will be volunteering their time.

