PROTOCOL TITLE:

Alcohol and Violence Prevention for College Students

PRINCIPAL INVESTIGATOR:

[name]

Sample Size and Analyses

Sample size for the randomized pilot trial was determined, using PASS©, to estimate the variability within a reasonable margin of error. This calculation also accounted for the low base rates of SA and 20% attrition. To estimate variability using a 95% two-sided confidence interval, within a margin of error of 80%, 53 total participants are needed. (For example, if the standard deviation is 10, the confidence limits would be 7 to 15. To design a future trial if we wanted to be conservative, we will use a standard deviation of 15.) We further adjusted the sample size considering low base rate and attrition. SA victimization is a low base-rate experience with a total of 60% of college women who engaged in HED reporting at least one SA victimization experience within a 3-month follow-up period¹². To account for this low base-rate experience, a total of 132 participants are needed. Preliminary studies by the research team estimate that there will be 20% attrition over a 3-month follow-up period, therefore, the final sample size for this pilot study will be 162 (n = 54 per risk group) to account for attrition rates.

We will perform secondary analyses using linear mixed model ANOVAs to determine the factors that potentially predict outcomes including alcohol use, SA victimization, and bystander intervention.

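### The SAP names only a marginal outcome SD for planning the future trial; the pilot should also estimate the baseline-to-3-month correlation and the SD that matches the future analysis

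*SAP*

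**What the plan says.** Protocol section 1.0 presents Aim 3 as a pilot to observe effect sizes and variability for a later randomized trial, and says of its size: "Sample size was determined to estimate the variability within a reasonable margin of error".

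The SAP (Sample Size and Analyses) sets the precision target: "To estimate variability using a 95% two-sided confidence interval", "within a margin of error of 80%, 53 total participants are needed". A parenthetical example follows: "if the standard deviation is 10, the confidence limits would be 7 to 15". It ends with the only statement in either document about what variance figure goes forward: "To design a future trial if we wanted to be conservative, we will use a standard deviation of 15".

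Protocol section 10.0 (Aim 3) has all participants complete a baseline survey on alcohol use, sexual assault and bystander items before randomization. It then says "The follow-up survey will be exactly the same as the baseline survey", with an exception in the same sentence: the questions at follow-up refer to the past three months.

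The SAP also plans linear mixed model ANOVAs, as secondary analyses of factors that may predict outcomes. It does not say that baseline enters those models as a wave or covariate. Neither document mentions a baseline-to-follow-up correlation, a residual SD or baseline adjustment.

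**The concern.** A marginal SD is the right planning input for one analysis only: an unadjusted comparison of 3-month scores. A trial that measures the same outcome at baseline and follow-up will often adjust for baseline, or test change. In both cases the required sample size depends on r as well as on the SD. Supplying planning variability is the main purpose of Aim 3, and the SD alone leaves that deliverable incomplete. Whoever designs the next trial would have to guess r without an interval, although the pilot's two surveys could have given one.

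**Working it through.** **Inputs.** From the SAP: 95% two-sided interval, n = 53, example SD 10 with limits 7 to 15, carried-forward SD 15, final n = 162, 20% attrition. Expected completers: 162 × 0.80 = 129.6, about 130; per risk group 54 × 0.80 = 43.2, about 43. Assumed, because the documents do not give them: r = 0.3, 0.5 or 0.7; for illustration only, a difference of 5, 80% power and two-sided 5%.

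**1. The plan's own limits.** SD limits are s × √[(n − 1)/χ²]. With n = 53 the χ² quantiles on 52 degrees of freedom are 73.81 and 33.97.
- For an SD of 10: 10 × √(52/73.81) = 8.39 and 10 × √(52/33.97) = 12.37.
- For a variance of 10: 10 × 52/73.81 = 7.05 and 10 × 52/33.97 = 15.31.

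The stated 7 to 15 is therefore not reproduced as SD limits, but it matches variance limits. Taking 15 as the SD inflates the variance by (15/12.37)² = 1.47, whatever r is. This is a separate error. SD 15 is kept below only because it is the SAP's figure; the ratios do not depend on it.

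**2. Future trial adjusts for baseline** (ANCOVA, or a mixed model with baseline means constrained equal). N is proportional to SD² × (1 − r²).

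**3. Future trial tests change, or an arm-by-time contrast with baseline means unconstrained.** With equal SDs at the two waves, N is proportional to SD² × 2(1 − r).

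For an unadjusted comparison, n per arm = 2 × (1.96 + 0.84)² × 15²/5² = 141.1; unrounded normal quantiles give 141.3, so 142.

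| r | 1 − r² | N overstated by 1/(1 − r²) | adjusted SD replacing 15 | n per arm, adjusted | 2(1 − r) | SD of change replacing 15 |
|---|---|---|---|---|---|---|
| 0.3 | 0.91 | 1.10 | 14.3 | 129 | 1.4 | 17.7 |
| 0.5 | 0.75 | 1.33 | 13.0 | 106 | 1.0 | 15.0 |
| 0.7 | 0.51 | 1.96 | 10.7 | 73 | 0.6 | 11.6 |

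At r = 0.3 a change or arm-by-time analysis would need 141.3 × 1.4 = 197.8, so 198 per arm against 142. The marginal SD is then too small, even though the SAP calls it conservative.

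**4. Can the pilot estimate r?** Fisher interval: tanh[atanh(r) ± 1.96/√(n − 3)]. With n = 130:
- r = 0.3: 0.13 to 0.45; at the lower limit 1 − r² = 0.98, a 2% saving.
- r = 0.5: 0.36 to 0.62; at the lower limit 0.87, a 13% saving.
- r = 0.7: 0.60 to 0.78; at the lower limit 0.64, a 36% saving.

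Within one risk group (n = 43), r = 0.5 has an interval of 0.23 to 0.70, and the saving at the lower limit is about 6%.

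**The case against.** The strongest reply is that the harm is hypothetical. The documents give no primary outcome, analysis model, target difference or r for the future trial. If it compares unadjusted 3-month scores, the marginal SD is the correct input. The figure of 15 sits in an example and is worded as what a cautious planner would use. Nothing is lost either: r can be computed from the retained data whenever the next trial is designed, and a mixed model fitted to both waves would produce it. All of this stands, and it limits the point to an improvement in what the pilot is committed to deliver. It does not show that the SAP already covers r, because the SAP neither says that baseline is modelled nor that any correlation will be reported.

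A reader might infer three stronger things that the documents do not support:
- That the future trial will be oversized. This needs a baseline-adjusted analysis and an r well above zero, and neither is stated. With a change or arm-by-time contrast and r below 0.5 the error runs the other way.
- That any two-wave mixed model gains the factor 1 − r². Only a baseline-constrained one does.
- That the saving extends to sexual assault victimization. The SAP describes that outcome by a proportion ("a total of 60% of college women who engaged in HED reporting at least one SA victimization experience"), so the formula does not carry over directly.

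Two limits on the gain are also fair. Fisher's interval assumes roughly bivariate normal scores, which drinking measures may not follow. And the pilot's r transfers only if the future trial uses the same look-back periods at both waves.

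**Conclusion.** The point holds conditionally. The SAP's only named variance input for the future trial is the upper limit of a marginal SD, which suits one of three plausible analyses. If the future trial adjusts for baseline, N is overstated 1.10 to 1.96 times for assumed r of 0.3 to 0.7. If it tests change, N is understated when r is below 0.5, by a factor of 1.4 at r = 0.3. Because r and the future analysis are unknown, the SAP's figure cannot be called conservative or wasteful; the pilot should estimate r in either case. About 130 completers give a usable interval when r is 0.5 or more and little gain when r is about 0.3. Nothing in the pilot's own inference is invalidated. The point applies to the continuous alcohol-use and bystander outcomes only.

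**What to change.** In the SAP, replace the sentence that carries the SD forward with text such as:

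> For the continuous alcohol-use and bystander outcomes we will estimate, on the analysis scale and each with a 95% confidence interval, the marginal SD at 3 months, the pooled within-arm correlation between baseline and 3 months, the residual SD after baseline adjustment, and the SD of change. The future trial will be sized on the upper 95% limit of the SD that matches its primary analysis: the residual SD if it adjusts for baseline, the SD of change if it tests change or an arm-by-time contrast, and the marginal SD if it compares unadjusted 3-month scores.

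Taking the upper limit of the matching SD keeps the SAP's cautious intent and avoids combining limits for two separate parameters.

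Separately, correct the example: for an SD of 10 at n = 53 the limits are 8.4 to 12.4.

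The cost is a short SAP edit, with no new data, visits or participants. The report should state the look-back period used at each wave, and give estimates by risk group only with their wider intervals.

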4.0 Study Endpoints

Outcome variables include alcohol use, bystander behavior, and sexual assault victimization 3-months after the intervention. Further, self-blame will be assessed directly after receiving the intervention to ensure that the intervention does not have iatrogenic effects (even though previous iterations of this intervention have found no iatrogenic effects).

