5.0 Inclusion and Exclusion Criteria/ Study Population

College students aged 18-25 will be recruited from Arizona State University (no participants will be recruited until an inter-institutional agreement is signed by Arizona State University, submitted as an amendment to the MUSC IRB and approved by the MUSC IRB) to complete questionnaires regarding their attitudes and behaviors related to alcohol use, sexual assault victimization, sexual assault perpetration, and bystander intervention. Human subjects are also being recruited to participate in an open pilot and a randomized pilot to determine usability as well as estimate effect size for a larger grant. In Aim 1a, we will recruit 750 college students aged 18-25 (n= 250 women; n=250 men; n=250 sexual/gender minorities) from both Arizona State University (data already collected and have de-identified dataset) and Georgia State University. In this aim, human subjects are needed to assess setting-specific normative attitudes and behavior for alcohol use and sexual assault to incorporate into the intervention content. Aim 1b includes alpha testing of a workbook version of the intervention, which will include interviews with key stakeholders (college administrators and 15 students) to inform programming content at both Arizona State University (data already collected and have de-identified dataset) and Georgia State University. In Aim 2, we will recruit 30 students (10 from each risk group (cisgender heterosexual men, cisgender heterosexual women, and sexual/gender minorities) who engage in heavy episodic drinking in the past month to participate in an open pilot trial to obtain usability feedback to integrate into the intervention content. In Aim 3, which will only be collected from Arizona State University, we will recruit 54 students who engage in heavy episodic drinking in the past month from each risk group (cisgender heterosexual men, cisgender heterosexual women, and sexual/gender minorities) for a total of 162 students aged 18-25 to participate in a randomized pilot trial. Aim 3 focuses on observing effect sizes and estimating the variability using a 3-month follow-up design to design a larger study for an R01 application. In this IRB application at Georgia State University, a total of 967 participants will be recruited (Aim 1a = 750 students from GSU, Aim 1b = 25 [25 students and 10 administrators] from GSU, Aim 2 = 30 students from GSU, Aim 3 = 162 students from ASU).

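### The SAP's step from 53 to 132 participants has no stated formula and is not reproduced by its stated 60% sexual assault rate

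*SAP*

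**What the plan says.** The derivation is in the SAP, Sample Size and Analyses, and has three steps.

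- **Precision.** "To estimate variability using a 95% two-sided confidence interval, within a margin of error of 80%, 53 total participants are needed".
- **Base rate.** The SAP reports "a total of 60% of college women who engaged in HED reporting at least one SA victimization experience within a 3-month follow-up" and continues: "To account for this low base-rate experience, a total of 132 participants are needed".
- **Attrition.** It takes 20% loss over three months; "therefore, the final sample size for this pilot study will be 162", with 54 per risk group.

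No formula is printed for the second step. Nor does either document give a 40% SA rate, or a three-month SA rate for men or for sexual and gender minorities.

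The protocol relies on the result. Section 1.0, Aim 3, refers to the variability target, low SA base rates and attrition, and adds: "This led to a sample size of 162 students". Section 5.0 fixes the split: "we will recruit 54 students who engage in heavy episodic drinking in the past month from each risk group".

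**The concern.** A reader who follows the paragraph with its own inputs does not reach 132. An adjustment for an event that only some participants experience normally divides the required number by the event proportion, and at 60% that gives a much smaller total. The text also calls a rate reported by a majority of women low, which suggests that the rate and the calculation may not belong together.

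A second gap is the population. The rate comes from women with heavy episodic drinking (HED), while women in the cisgender heterosexual group are one third of the planned sample. Using the rate for the whole sample is an assumption that the SAP does not state.

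At stake is whether the sample-size justification can be reproduced. SA victimization is one of the named outcomes (Protocol 4.0: "Outcome variables include alcohol use, bystander behavior, and sexual assault victimization 3-months after the intervention"), and its base rate is the only reason given for going from 53 to 132.

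**Working it through.** **Inputs**, all from the SAP, Sample Size and Analyses: starting number 53 (taken as given here), SA rate 60%, number after the base-rate step 132, attrition 20%, final number 162 in three groups of 54.

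**1. What reproduces 132?** The implied divisor is 53/132 = 0.402, and 53/0.40 = 132.5, which is 132 truncated or 133 rounded up. A divisor of 0.40 can be a rate of about 40%, or the complement of the printed rate, 1 - 0.60 = 0.40.

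**2. What does the printed rate give?** 53/0.60 = 88.3, so 89. The printed 132 is 132 - 89 = 43 higher (43/89 = 48%).

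**3. Other uses of 60%.** None of these gives 132:

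- 53 × 1.6 = 84.8
- 53 × 1.4 = 74.2
- 53/0.60/0.80 = 110.4
- 53/(0.60 × 0.60) = 147.2
- 53/(0.60 × 0.40) = 220.8

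**4. A route without the SA rate.** 2 × 53/0.80 = 132.5. This would treat 53 as a per-arm number and take attrition at this step.

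**5. The attrition step.** 132/0.80 = 165. The common shortcut 132 × 1.20 = 158.4 does not give 162 either. Working back, 162 × 0.80 = 129.6, so about 130 retained, not 132. The discrepancy is small.

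**6. The whole chain under each divisor**, rounding up at each step:

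| Divisor | Retained | Enrolled at 20% attrition | Enrolled, three equal groups |
|---|---|---|---|
| 0.60 | 53/0.60 = 88.3, so 89 | 89/0.80 = 111.25, so 112 | 114 |
| 0.40 | 53/0.40 = 132.5, so 133 | 133/0.80 = 166.25, so 167 | 168 |
| SAP as printed | 132 | 162 | 162 |

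**7. What 162 delivers.** With 129.6 retained, the expected number reporting SA is 129.6 × 0.60 = 77.8 (about 78) at 60%, or 129.6 × 0.40 = 51.8 (about 52) at 40%. Both assume that one rate holds in all three groups.

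**The case against.** The strongest reply is that 89 appears nowhere in the plan. It exists only if the adjustment is division by the rate, and the SAP prints no such formula. Another method could have produced 132 legitimately, and step 4 shows that one other route lands on the same value. This stands in part: 89 is conditional, and it would be too strong to say that either the rate or the divisor must be wrong. But the step 4 route does not match what is written. The SAP says "53 total participants are needed", attributes 132 to the base rate, and applies attrition afterwards. If that route was used, the described method is the part that is misstated.

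A second reply is that this is a pilot sized to estimate variability, not to power a test, and that 162 serves it under either divisor. That is right as to consequences: 162 exceeds 112 by 50, or leaves about 52 reporters against 53. It does not repair the derivation.

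A third reply is that the women-only rate is a separate matter of generalizability, and that Protocol 2.0 places the highest victimization rates among women and sexual/gender minorities. That gives some support for a similar rate in the minority group. It gives none for men, and the SAP still does not state the assumption.

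**Conclusion.** The point holds. The step from 53 to 132 has no stated formula, and the stated 60% does not reproduce it. Under division by the base rate, the printed rate supports 89 retained and 112 enrolled, against 132 and 162 in the SAP. The figure 132 fits a divisor of 0.40. The rate, the divisor or the described method is misstated. Separately, 162 is 3 short of the 165 that 132 requires at 20% attrition.

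Three stronger readings are tempting, and the documents support none of them.

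- **That 60% is a misprint for 40%.** Calling the event low base-rate fits this, but division by the complement of a correct 60% gives the same 132.
- **That the trial is the wrong size.** At 60% the sample is larger than the calculation needs; at 40% it falls just under. For alcohol use and bystander behavior, about 130 retained is well above 53.
- **That a wrong rate will pass into the later trial.** Protocol 1.0 plans that trial from the effect sizes and variability observed in this pilot, and neither document says that the 60% or the divisor will be reused.

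The effect is limited to the written sample-size justification. Confidence is high that the printed figures do not agree with the stated rate; which one is at fault cannot be settled from the documents.

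**What to change.** Keep 162 and change nothing in conduct. Check the source cited for the SA rate, then restate the SAP derivation so that the rate, the formula, 132 and 162 agree:

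- **If 60% is right and is the intended divisor:** state 89 retained and 112 enrolled (114 for three equal groups), and note that 162 exceeds this.
- **If the divisor is a 40% rate:** correct the 60%, and state that the calculation needs 133 retained and 167 enrolled (168 for equal groups), so that 162 gives about 130 retained and about 52 reporters, just under 53.
- **If another method produced 132:** give its formula and inputs.

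In every case, correct the attrition step: if 132 is kept, 20% attrition leads to 165, and 162 is expected to retain about 130. Say whether 53 means participants or participants reporting SA. Add one sentence that the rate comes from college women with HED and that applying it to the other risk groups, men in particular, is an assumption.

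The cost is a source check and a few lines of SAP wording, with no added participants.
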